6.2 STUDY SUBJECTS

6.2.1 Subject disposition

Normal completion as well as early discontinuation will be described on the ITT population. Reasons for withdrawals and normal completions will be summarized using frequency distribution (n, %). All withdrawals will be detailed in a subject-by-subject listing.

6.2.2 Protocol deviation

Major protocol deviations will be summarized using frequency distribution (n, %) detailed in a subject-by-subject listing.

6.2.3 Data sets analyzed

Number of subjects included in each efficacy analyses (PP, ITT) and number of patients included in the safety analysis (APT) will be presented by parallel group and overall.

6.2.4 Demographic data

Demographic data collected at baseline will be descriptively summarized for ITT population by parallel group and overall.

6.2.5 Rosacea co-morbidities and Medical history

Rosacea co-mobordities and medical history defined as the relevant or major illnesses not previously reported as co-mobordities present before the baseline visit will be presented separately by System Organ Class and preferred term (MedDRA).

6.2.6 Medical history of acute rosacea (worsening)

Facial rosacea duration will be descriptively summarized on the ITT population, by duration classes, study group and overall.

History of flushing or worsening of erythema will be descriptively summarized on the ITT population using frequency distribution (n, %), by type of stimuli triggers, study group and overall.

6.2.7 Previous and concomitant drug and procedure therapies

Previous drugs/procedures therapies are defined as drugs/procedures stopped on or before the baseline visit. Concomitant drugs/procedures are defined as drugs/procedures occurred between the baseline visit and the last visit. Previous and Concomitant drugs/procedures will be descriptively summarized on the ITT population, by Anatomical-therapeutic-chemical (ATC) text level 5 and drug name for drugs and by SOC and preferred term for procedures, by study group and overall. Frequency distribution of subjects with at least one previous drug/ procedure at baseline and/or with at least one concomitant drug/procedure will be tabulated (n, %).

6.2.8 Compliance

Compliance of investigational products (oral and topical) will be calculated from the data captured at every visit and will be summarized by group in terms of frequency counts and percentages by products and for the association of investigational products. The compliance will be calculated as follows:

Compliance= ((Date of last visit - Date of baseline) - total number of missing applications)*100 (Date of last visit - Date of baseline).

Compliance of the moisturizer will be also calculated as follows:

Moisturizer compliance = $\underline{\text{Total number of days where the moisturizer was used *100}}$ (Date of last visit – Date of baseline)

6.2.9 Baseline disease characteristics

The characteristics of the disease collected at baseline will be descriptively summarized on ITT population by parallel group and overall.

6.3 EFFICACY ANALYSES

6.3.1 Primary efficacy analyses

The primary objective of this study was to demonstrate the superiority of the IVM/Doxy compared to IVM/Placebo, in terms of percent change from baseline in inflammatory lesion count at week 12.

The primary efficacy endpoint will be analyzed by using the Cochran-Mantel-Haenszel (CMH, FREQ procedure from SAS®) statistic, stratified by center (or analysis-center) after ridit transformation with the row mean difference statistics, testing the hypothesis of equality on ITT/LOCF population. PP analysis will also be performed to assess the robustness of the results obtained on ITT/LOCF population. The p-values will have to be inferior to 0.05 at week 12.

6.3.2 Secondary and other efficacy analyses

The variables will be analyzed similarly as primary analyses on ITT/LOCF population at each post-baseline evaluation time on appropriate population.

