5.4 CLINICAL TRIAL FLOW CHART

	STUDY VISITS			
PROCEDURES	Visit 1	Visit 2	Visit 3	Visit 4
	Screening/ Baseline	Week 4	Week 8	Week 12
		(±3 d)	(±3 d)	(±5 d)
Informed Consent/Photography Consent	Х			
Inclusion/Exclusion Criteria	Х			
Demographics/Medical History (including	Х			
flushing and co-morbidities) / Previous Therapies (including rosacea last treatment)				
Concomitant Therapies	Х	Х	Х	Х
Urine Pregnancy Test (UPT) ^a	Х			X
Inflammatory (Papules and Pustules) Lesion Counts	X	Х	Х	X
Clinician Erythema Assessment (CEA)	Х	Х	Х	Х
Investigator's Global Assessment (IGA)	Х	Х	Х	Х
Severity of Stinging/Burning sensation	X	Х	Х	X
Global assessment of Ocular signs and symptoms	Х	Х	Х	Х
Flushing via diary (frequency and severity)	Х	Х	Х	Х
Subject's Global Improvement in Rosacea				X ^d
Standardized Facial photography / facial redness colorimetric measurements ^b	X	Х	Х	X
Adverse Event (AE) ^c	Х	Х	Х	Х
DLQI Questionnaire	Х			X ^d

Protocol N° RD.03.SPR.113322

version Final dated 10-FEB-2017

Page 43 of 106 CONFIDENTIAL

EQ-5D-5L Questionnaire	Х			X ^d
WPAI: GH questionnaire	Х			X ^d
Subject Satisfaction Questionnaire				X ^d
Dispensation of Investigational Products, Subject Diary and Other Supplies	Х	Х	Х	
Return of Investigational Products and Subject Diary		Х	Х	Х
Exit form				Xď

a. For subjects of childbearing potential only. UPT is mandatory at Screening/Baseline and at last visit (Week 12 or before if early termination).

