9.1.4 Statistical analyses

Any changes of the statistical analyses decided after the database lock will be justified and documented.

The definition of the populations will be finalized after a blind data review meeting, during which the distribution of subjects per site will be reviewed. In case of too small sites or in case of severe unbalance between the size of sites, some sites may be combined, e.g. per geographical area, to form analysis-center for purpose of stratification of the statistical analyses.

The primary objective of this study will be to demonstrate the superiority of the Ivermectin 1% topical cream associated with Doxycycline 40 mg MR capsules compared to versus Ivermectin 1% topical cream associated with Placebo, in terms of Inflammatory Lesion count at week 12.

The primary efficacy endpoint will be analyzed by using the Cochran-Mantel-Haenszel (CMH, FREQ procedure from SAS®) statistic, stratified by center (or analysis-center) after ridit

Protocol N° RD.03.SPR.113322

version Final dated 10-FEB-2017

Page 77 of 106 CONFIDENTIAL

transformation with the row mean difference statistics, testing the hypothesis of equality on ITT/LOCF population. PP analysis will also be performed to assess the robustness of the results obtained on ITT/LOCF population. The p-values will have to be inferior to 0.05 at week 12.

The secondary efficacy variables, questionnaires will be analyzed similarly as primary analyses on appropriate population.

The subject characteristics (disposition, previous and concomitant therapies, study treatments duration/ compliance, demographics, baseline characteristics,...), lesion counts and adverse event(s) will only be summarized descriptively, on appropriate population.

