4.2 PATIENT-REPORTED OUTCOMES VARIABLES

> Dermatology Life Quality Index (DLQI) at week12/early termination: % of subject across Total score at baseline and last visit; and the % change from baseline.

Grade	Description
0-1	No effect at all on patient's life
2-5	Small effect on patient's life
6-10	Moderate effect on patient's life
11-20	Very large effect on patient's life
21-30	Extremely large effect on patient's life

- ➤ EQ-5D questionnaire at week12/early termination: % of subjects across score of questions at baseline and last visit.
- > Work Productivity and Activity Impairment Questionnaire at week 12/early termination: General Health (WPAI: GH) modified for Rosacea. % of subjects across score of questions at baseline and last visit.
- > Subject's satisfaction questionnaire at week12/early termination: % of subjects across score of questions at last visit.

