5.4 MISSING VALUES

In order to evaluate the effect of major deviations or of data exclusions, the last observation carried forward (LOCF) method will be used to impute missing values for inflammatory lesion count and IGA. If no post-baseline data are available, baseline will be carried forward. Thus, the number of subjects will not vary at each visit. The other missing values will not be replaced (observed data).

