6.4 PATIENT-REPORTED OUTCOMES ANALYSES

DLQI, EQ-5D-5L, WPAI-GH and subject satisfaction questionnaires will be statistically analyzed similarly as primary analyses on ITT population at each post-baseline evaluation time.

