7. CHANGES FROM THE PROTOCOL ANALYSIS PLAN

The Percent of subject clear inflammatory lesions (100% reduction of IL) at each post-baseline visit will be analyzed.

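### Six outcome measures with a collected baseline are tested on post-baseline scores without baseline adjustment, which gives up some power but not validity

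*SAP*

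**What the plan says.** SAP 6.3.1 defines the primary test as a CMH statistic "stratified by center (or analysis-center) after ridit transformation with the row mean difference statistics". No baseline term appears. SAP 6.3.2 extends it: "The variables will be analyzed similarly as primary analyses on ITT/LOCF population at each post-baseline evaluation time on appropriate population". SAP 6.4 states that the four questionnaires "will be statistically analyzed similarly as primary analyses on ITT population at each post-baseline evaluation time". Protocol 9.1.4 gives the same instruction: "The secondary efficacy variables, questionnaires will be analyzed similarly as primary analyses on appropriate population".

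The shells show what is tested:

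- **Tables 19 (CEA), 21 (stinging/burning) and 23 (ocular signs):** the visit score has a p-value, and the baseline p-value is marked NA.
- **Tables 33 (EQ-5D-5L) and 35 (WPAI:GH):** the last-visit items have p-values. Baseline appears only in the descriptive Tables 32 and 34.
- **Table 31 (DLQI):** one p-value for the last-visit total and a second for percent change from baseline.

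Baseline is collected for all of these. The protocol 5.4 flow chart schedules each assessment at Screening/Baseline, SAP Table 14 summarises the three clinical scores there, and SAP 4.2 describes EQ-5D and WPAI as percentages "of subjects across score of questions at baseline and last visit".

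On missing data, protocol 9.1.2.4 applies LOCF to lesion count, CEA, IGA and stinging/burning, with baseline carried forward if nothing later exists. SAP 5.4 limits LOCF to lesion count and IGA and leaves other values as observed. Tables 19 and 21 are nevertheless labelled ITT/LOCF. SAP section 7 lists one change from the protocol: "The Percent of subject clear inflammatory lesions (100% reduction of IL) at each post-baseline visit will be analyzed".

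**The concern.** A subject's score before treatment usually predicts the score after it. Comparing post-baseline scores alone leaves that predictable variation in the noise. Adjusting for baseline within the same center-stratified ridit framework removes part of it, using data already in the case report form. What is at stake is power on secondary, exploratory and patient-reported outcomes.

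Several outcomes are not affected:

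- The primary and other lesion-count analyses, flushing and colorimetry are already expressed relative to baseline.
- IGA is grade 4 for everyone at entry, so its baseline carries no information.
- Subject's Global Improvement has no baseline value.

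**Working it through.** **Inputs from the documents.** Two-sided 0.05 (SAP section 6); 135 per arm, 1:1 (protocol 5.1 and 9.2.2, SAP 3.2.2); the test (SAP 6.3.1). **Assumed, because no document gives them:** the baseline-to-visit correlation r, category shares, the number of analysis-centers, and a starting power of 80%.

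**1. The plan's own figure (primary endpoint only).** n per arm = 2 × (1.960 + 1.282)² × (35/15)² = 2 × 10.51 × 5.444 = 114.4, so 115 after rounding up; the stated 114 gives 89.9% power. 114/0.85 = 134.1, so 135. The figure reproduces to within one subject. The plan states no power for the endpoints at issue.

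**2. Formula.** Baseline adjustment multiplies the residual variance by 1 − r². An 80% start means a standardised signal of 1.960 + 0.842 = 2.802, i.e. 2.802 × √(2/135) = 0.341 SD. Power becomes Φ(2.802/√(1 − r²) − 1.960), equivalent to 1/(1 − r²) times the subjects.

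| r | Power | Equivalent subjects |
|---|---|---|
| 0 | 80.0% | 1.00 |
| 0.1 | 80.4% | 1.01 |
| 0.3 | Φ(2.802/0.954 − 1.960) = 83.6% | 1.10 |
| 0.5 | Φ(2.802/0.866 − 1.960) = 89.9% | 1.33 |

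A plain change score is not a substitute. Its variance factor is 2(1 − r), so power is 65.8% at r = 0.3 and only returns to 80% at r = 0.5.

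**3. Ordinal check by simulation.** 135 per arm, 1:1 within stratum, modified ridits, one pooled slope, 4,000 trials per setting, 12 strata unless stated. For a four-level score away from the floor (latent shift 0.37 SD), power unadjusted/adjusted was:

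| Strata | Observed r 0.33–0.34 | Observed r 0.50–0.51 |
|---|---|---|
| 6 | 79.3/84.0% | 79.8/90.1% |
| 12 | 78.5/83.4% | 78.2/89.2% |
| 27 | 78.2/82.3% | 77.8/88.7% |

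**4. CEA.** IGA grade 4 already describes severe erythema (protocol 7.1.3), and Table 14 lists only baseline CEA grades 3 and 4. With grade-3 shares of 5, 15, 30 and 50%:

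- Latent r 0.3: 78.7% becomes 78.9, 79.5, 80.3 and 81.1%.
- Latent r 0.5: 78.8% becomes 80.3, 82.1, 83.9 and 85.0%.

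The gain is 0 to 6 points.

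**5. Floor-heavy four-level item.** With 70, 85 and 95% at the lowest grade at baseline:

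- Latent r 0.3: 82.0/83.3, 81.7/83.4 and 82.6/82.8%.
- Latent r 0.5: 82.1/86.5, 82.0/85.6 and 82.2/83.6%.

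The gain is 0.2 to 4.4 points.

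**6. Missing baseline** (latent r 0.6, missing at random; unadjusted test on all subjects 79.2%):

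| Baseline missing | Set to stratum mean ridit | Subject dropped |
|---|---|---|
| 5% | 89.9% | 89.0% |
| 10% | 89.5% | 87.0% |
| 20% | 88.1% | 82.1% |
| 30% | 86.8% | 75.8% |

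At 30% missing, dropping subjects is worse than not adjusting.

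**7. Type I error.** Under no effect, rejection was 4.4–5.2% unadjusted and 4.1–5.4% adjusted.

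**The case against.** The strongest reply is that this is a preference. Protocol 9.1.1.2 defines CEA and stinging/burning as distributions of scores at each visit, protocol 9.1.4 asks for the primary method, and the SAP and shells deliver it. That stands: the tests are valid under randomisation, and the size rests on correlations nobody has supplied. It does not remove the point, because the gain costs nothing in data.

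Three stronger readings are tempting and not supported:

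- **Treatment differences are estimated less precisely.** The affected tables plan arm summaries and a p-value, with no difference or confidence interval. What is lost is power.
- **Baseline is never used.** Table 31 tests DLQI percent change. Under protocol 9.1.2.4, a subject with no post-baseline CEA or stinging/burning score contributes the baseline as the tested value. Whether that applies is unclear, because SAP 5.4 differs.
- **Table 36 ranks *Never treated* below *Worse*.** The shell gives display order without codes, whereas Table 29 codes its *Not relevant* answer as 0. No ranking rule is stated, and an analyst would sensibly exclude the answer. *Not applicable* appears in items 4 and 5 of protocol Attachment 4, which the abbreviated shell does not print. This is missing detail only.

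Two limits apply to the simulations. Subjects not employed skip the WPAI work questions, so those items have fewer subjects and structurally missing baselines. The synopsis limits ocular assessment to signs present at baseline, while protocol 5.4 and 7.1.5 assess at each visit without that limit; if the synopsis governs, both the number of subjects and the floor scenario change.

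**Conclusion.** The concern holds as a minor efficiency point. The planned tests for these six measures are valid, no decision rule depends on them, and the primary analysis and sample size are untouched. They give up some power by not adjusting for collected baseline scores: about 4 points from 80% at an assumed r of 0.3 and about 10 points at 0.5. The gain approaches zero for CEA when few subjects enter at grade 3 and for items crowded at the lowest grade. For DLQI the point concerns only the last-visit total. Separately, protocol 9.1.2.4 and SAP 5.4 disagree on LOCF for CEA and stinging/burning. The Table 36 answers need a clarifying note and do not add to the weight of the point.

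**What to change.** 1. **SAP 6.3.2 and 6.4:** specify a center-stratified rank-ANCOVA CMH for CEA, stinging/burning, ocular signs, DLQI total, EQ-5D-5L and the scored WPAI items, leaving out the yes/no employment item. Regress within-stratum ridits of the post-baseline score on baseline ridits with one slope pooled across analysis-centers, then apply the same row-mean-score test to the residuals.
2. **Missing baseline:** assign the stratum mean baseline ridit (0.5 for modified ridits), including for WPAI work items skipped at baseline, so that no subject now in the test is lost.
3. **SAP section 7:** record the change, since protocol 9.1.4 names the primary method for these variables.
4. **LOCF:** reconcile protocol 9.1.2.4 with SAP 5.4 for CEA and stinging/burning, and label Tables 19 and 21 to match.
5. **Table 36, clarification only:** footnote that *Never treated* (item 12) and *Not applicable* (items 4 and 5) are tabulated but left out of the ridit test.

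The cost is a few sentences, one change entry, a footnote and a few lines of programming, with no new data. Protocol 9.1 requires the SAP to be final before database lock and unblinding. The SAP is dated 12 April 2018, after the planned last subject out in Q1 2018, and the documents do not show whether lock had occurred. A change to the finalised SAP must be documented in the clinical trial report under the same section.

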6.4 PATIENT-REPORTED OUTCOMES ANALYSES

DLQI, EQ-5D-5L, WPAI-GH and subject satisfaction questionnaires will be statistically analyzed similarly as primary analyses on ITT population at each post-baseline evaluation time.

6.5 SAFETY ANALYSES

6.5.1 Extent of exposure

6.5.1.1 Treatment duration

Treatment duration will be calculated as the number of days between the date of first use and the date of the last use of each study treatment (oral and topical). In case of missing data of last use, the last visit will be taken into account.

6.5.2 Adverse Events

The adverse events will be summarized (n, %) for APT population by parallel group. Deaths and serious adverse events will be reported as well as withdrawals due to adverse events. In case of worsening of rosacea, a specific questionnaire was filled on and the results will be listed.

7. CHANGES FROM THE PROTOCOL ANALYSIS PLAN

The Percent of subject clear inflammatory lesions (100% reduction of IL) at each post-baseline visit will be analyzed.

APPENDIX 1: LIST AND FORMAT OF TABLES

GENERAL FEATURES

• Margins for portrait orientation

 Top 	= 3.71 cm
 Bottom 	= 3.17 cm
• Left	= 3 cm
 Right 	= 1.4 cm
 Heading 	= 2.41 cm
 Footnote 	= 2.16 cm

• Margins for landscape orientation

```
    Top = 3 cm
    Bottom = 1.4 cm
    Left = 3.17 cm
    Right = 3.71 cm
    Heading = 2.16 cm
    Footnote = 1.25 cm
```

8. TABLE SHELLS

14.1. Study Subjects

14.1.1. Conduct of the study

Table 1. Enrolment by analysis center and investigational site (ITT)

	IVM + Doxycycline (N=xxx)	IVM + Vehicle (N=xxx)	Total (N=xxx)
Analysis-Center 1 (n,%) Center 1 (n,%)			
Analysis-Center 2 (n,%)			

Table 2.1. Subjects who discontinued study and reason for discontinuation (ITT)

	IVM + Doxycycline	IVM + Vehicle	Total
	(N=xxx)	(N=xxx)	(N=xxx)
Randomized			
Normal study completion n (%)			
Premature discontinuation n (%)			
Lack of efficacy n (%)			
Adverse event n (%)			

Table 2.2. Listing of subjects who discontinued treatment and reason for discontinuation (ITT)

 $(Include: treatment, investigator\ number, subject\ number\ and\ reason\ for\ discontinuation)$

Table 3. Adherence to the visit schedule in days (ITT)

	IVM + Doxycycline	IVM + Vehicle	Total
Nb of days between baseline visit and week 4 visit			
N			
Mean±SD			
Median			
(Min,Max)			
Nb of days between baseline visit and week 12 visit			
N			
Mean±SD			
Median			
(Min,Max)			
Nb of days between baseline visit and last visit			
N			
Mean±SD			
Median			
(Min,Max)			

Table 4.1. Major protocol deviations (ITT)

	IVM +	Doxycycline	IVM +	- Vehicle		Total
eg:	N.	% subj.	N	% subj.	N	% subj.
AT LEAST ONE MAJOR DEVIATION						
No post-Baseline data						
No study medication dispensed						

A subject may have several major protocol deviations

Numbers in columns cannot be added because a given subject may have reported more than one deviation.

Table 4.2. Listing of subjects with Major protocol deviations (ITT)

(Include: treatment, investigator number, subject number, reason and detail of deviations)

Table 5. Data sets analyzed

	IVM + Doxycycline	IVM + Vehicle	Total
Intent to treat population (ITT) n(%)			
Per Protocol population (PP) n(%)*			
Safety population (APT) n(%)*			

^{*} Denominator is the number of subjects in the Intent to treat population

14.1.2. Subject characteristics

Table 6. Demographic data (ITT)

	IVM + Doxycycline	IVM + Vehicle	Total
Gender			
N			
Male n(%)			
Female n(%)			
Age			
N			
18-65 years			
>= 65 years			
Mean ±SD			
Median			
Min,Max			
Race			
N			
White n (%)			
Black n (%)			
Ethnicity*			
N			
Hispanic or Latino n (%)			
Not hispanic or Latino n (%)			
•••			
Phototype			
N			
I n (%)			
II n (%)			

^{*} Ethnicity is optional for Canada and Europe

Table 7. Rosacea co-morbidities (ITT)

IVM + Doxycycline	IVM + Vehicle	Total
(N=xxx)	(N=xxx)	(N=xxx)
	, ,	(N=xxx) (N=xxx)

The numbers in the columns cannot be added because a given subject could report more than one co-morbidity

Table 8. Medical history other than co-morbidities (ITT)

	IVM + Doxycycline	IVM + Vehicle	Total
	(N=xxx)	(N=xxx)	(N=xxx)
Subjects reporting at least one medical history			
List all medical histories by SOC and preferred			
term			

The numbers in the columns cannot be added because a given subject could report more than one medical history

Table 9. Medical history of rosacea (ITT)

	IVM + Doxycycline	IVM + Vehicle	Total
For rosacea: duration in year			
N			
Less than 1 year n(%)			
Between 1 and 5 year n(%)			
More than 5 years n(%)			
Mean ±SD			
Median			
Min,Max			
History of flushing or worsening of erythema			
N			
No n(%)			
Yes n(%)			
Stimuli triggers			
Spicy food n(%)			

Table 10. Previous drug therapies within the previous 6 months, by ATC text and drug name (ITT)

	IVM + Doxycycline	IVM + Vehicle	Total
	(N=xxx)	(N=xxx)	(N=xxx)
Subjects reporting at least one previous therapy			
List all previous drugs by ATC and drug name.			

The numbers in the columns cannot be added because a given subject could report more than one previous therapy

Table 11. Previous procedure therapies within the previous 6 months, by System Organ class and Preferred Term (ITT)

IVM + Doxycycline
(N=xxx) (N=xxx) (N=xxx)
ast one previous procedure
dures by SOC and preferred term
1 1

The numbers in the columns cannot be added because a given subject could report more than one previous procedure.

Table 12. Concomitant drug therapies by ATC text and drug name (ITT)

	IVM + Doxycycline	IVM + Vehicle	Total
	(N=xxx)	(N=xxx)	(N=xxx)
Subjects with at least one concomitant medication			
List all concomitant drugs by ATC and drug name			

The numbers in the columns cannot be added because a given subject could report more than one concomitant therapy.

Table 13. Concomitant procedure therapies by System Organ Class and Preferred Term (ITT)

	IVM + Doxycycline (N=xxx)	IVM + Vehicle (N=xxx)	Total (N=xxx)
Subjects with at least one concomitant procedure			
List all concomitant procedures by SOC and preferred term			

The numbers in the columns cannot be added because a given subject could report more than one concomitant procedure.

Table 14. Baseline disease characteristics (ITT)

	IVM + Doxycycline	IVM + Vehicle	Total
	(N=xxx)	(N=xxx)	(N=xxx)
Facial inflammatory lesion counts			,
N			
Mean ±SD			
Median			
Min,Max			
Clinician's Erythema Assessment			
N			
3: Moderate n (%)			
4: Severe n (%)			
Mean ±SD			
Median			
Min,Max			
Investigator's Global Assessment			
N A G			
4: Severe n (%)			
Mean ±SD			
Median			
Min,Max Savarity Sears of Stinging/Burning			
Severity Score of Stinging/Burning N			
0: None n (%)			
1: Mild n (%)			
2: Moderate n (%)			
3: Severe n (%)			
Mean ±SD			
Median			
Min,Max			
Ocular Signs and Symptoms			
N			
0: None n (%)			
1: Mild n (%)			
2: Mild-Moderate n (%)			
3: Moderate-Severe n (%)			
4: Severe n (%)			
Mean ±SD			
Median			
Min,Max			
Number of flushing during the last week before			
baseline			
N Maria ISD			
Mean ±SD			
Median Min Mor			
Min,Max			
Average severity of flushing during the last week before baseline			
N N			
Mild n(%)			
Mild ii(%) Moderate ii(%)			
Severe n(%)			
Severe II(70)	l .		

